3.6 Risks and benefits

Secukinumab has shown efficacy in several inflammatory diseases, including PsA, AS, and psoriasis. The large safety dataset of secukinumab across indications involving over 8,200 patients did not show unexpected safety issues relative to the known mode of action. In general, secukinumab is safe and well-tolerated and has demonstrated a similar safety profile to etanercept and ustekinumab in two head-to-head comparison studies over one-year in psoriasis (Langley 2014; Thaci 2015). The most frequently reported AEs are non-serious mild to moderate infections, mainly upper respiratory tract infections. In addition, there is an increase in superficial candidiasis, mainly oral candidiasis, with secukinumab compared with placebo, but the cases were generally mild or moderate in severity, non-serious and responsive to standard treatment. There is also a small increase in neutropenia cases with secukinumab compared with placebo. Common Toxicity Criteria (CTC) AE grade 3 neutropenia (<1.0-0.5 x 10⁹/L) was uncommonly observed with secukinumab, and most cases were mild to moderate, transient and reversible and without a temporal relationship to serious infections. Hypersensitivity reactions include urticaria. Rare events of anaphylactic reaction to secukinumab have also been observed in clinical studies.

With adalimumab (Humira®), the most common adverse reactions (incidence >10%) across indications are infections (e.g. upper respiratory, sinusitis), injection site reactions, headache and rash (Humira® package insert; Humira® SmPC 2016). The most serious adverse reactions were serious infections including hepatitis B virus reactivation, neurologic or hematological reactions, autoimmune disorders and malignancies. In clinical trials of Humira®, allergic reactions overall (e.g., allergic rash, anaphylactoid reaction, fixed drug reaction, non-specified drug reaction, urticaria) were observed in approximately 1% of patients.

The immunogenicity potential, i.e. of eliciting anti-drug antibodies (ADA), is higher for adalimumab (up to 26%) than for secukinumab (<1%) (Humira® package insert; Cosentyx® package insert). However, the presence of ADAs does not appear to be associated with development of adverse reactions or lack of efficacy for both secukinumab and adalimumab.

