¹³ Subjects who discontinue the study should be scheduled for an End-of-Study study visit, 4 weeks after their last study treatment administration, at which time all of the assessments listed for the Week 52 visit will be performed. Subjects will return to the study site for the follow-up visits at 12 weeks and 18 weeks after last study treatment (assessments as listed for Week 60 and Week 68).S = assessment to be recorded on source documentation

^{*}The administration of s.c. study treatment may be done at site or at the subject's home by an independent drug administrator. Concomitant medication/non-drug therapy and Adverse Events/SAEs will be collected by telephone, if the administration of study treatment is done at home.

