6.5.5 Laboratory evaluations

A central laboratory will be used for analysis of all specimens listed below (except urinalysis). Details on the collection, shipment of samples and reporting of results by the central laboratory are provided in the laboratory manual. For the identification of clinically notable values, see Appendix 6 and Appendix 7. All subjects with laboratory tests containing clinically significant abnormal values are to be followed until the values return to normal ranges or until a valid reason, other than treatment related AE, is defined.

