In addition, shift tables will be provided for all parameters to compare a subject's baseline laboratory evaluation relative to the visit's observed value. For the shift tables, the normal laboratory ranges will be used to evaluate whether a particular laboratory test value was normal, low, or high for each visit value relative to whether or not the baseline value was normal, low, or high. These summaries will be presented by laboratory test and treatment group. Shifts will be presented by visit as well as for most extreme values post-baseline.

Vital signs

Analysis of the vital sign measurements using summary statistics for the change from baseline for each post-baseline visit will be performed. These descriptive summaries will be presented by vital sign and treatment group. Change from baseline will only be summarized for subjects with both baseline and post-baseline values.

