TBL	>1.5xULN, >2xULN, >3xULN,
ALP	>2xULN, >3xULN. >5xULN
ALT or AST & TBL	ALT or AST >3xULN & TBL >2xULN; ALT or AST >5xULN & TBL >2xULN; ALT or AST >8xULN & TBL >2xULN; ALT or AST >10xULN & TBL >2xULN
ALP & TBL	ALP >3xULN & TBL >2xULN ALP >5xULN & TBL >2xULN
ALT or AST & TBL & ALP	ALT or AST >3xULN & TBL >2xULN & ALP <2xULN (Hy's Law) Note: elevated ALP may suggest obstruction as a consequence of gall bladder or bile duct disease; ALP may also be increased in malignancy. FDA therefore terms Hy's Law cases as indicators of pure hepatocellular injury . This does not mean that cases of ALT or AST >3xULN & TBL >2xULN & ALP ≥2xULN may not result in severe DILI.

Notes:

1) In studies which enroll subjects with pre-existing liver disease, baseline LFT may be increased above ULN; in such a case it is meaningful to add the condition "and worse than baseline" to the abnormality criteria

For a combined criterion to be fulfilled, all conditions have to be fulfilled on the same visit. The criteria are not mutually exclusive, e.g. a subject with ALT = 6.42xULN is counted for ALT >3xULN and ALT >5x ULN.

Individual subject data listings will be provided for subjects with abnormal laboratory data. Data of subjects with newly occurring or worsening liver enzyme abnormalities will be listed in an additional listing.

Box plots over time will be presented for selected laboratory parameters (neutrophils, liver and lipid parameters).

In addition, three individual subject data listings will be provided for liver events, laboratory values and viral serology, autoimmunity, imaging, pathology, drug abuse for patients with liver events.

The laboratory values below Lower Level of Quantification (LLQ) or above Upper Level of Quantification (ULQ) will be imputed as LLQ or ULQ, respectively. The numerical part of the reported result will be treated as the actual LLQ or ULQ. These laboratory values will be displayed in listings using the standard unit with the reported sign (" $<$ " or " $>$ ")."

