6.1 Visit Windows

When visit windows are used, all visits will be re-aligned, i.e., they will be mapped into one of the visit windows. E.g., if the Week 4 visit of a subject is delayed and occurs on Day 46 instead of scheduled Day 29, say, it will be re-aligned to visit window *Week 8*. In the case of major deviations from the visit schedule, or due to unscheduled visits, several assessments of a subject may fall in a particular visit window (either scheduled or unscheduled).

For lab/ECG/vital signs, follow-up (F/U) visit is excluded from analysis visit mapping window. Only assessments that come as F/U nominal visit will be directly assigned as analysis F/U visit. Other assessments that are beyond the last on-treatment visit window (W50) or after nominal F/U visit date won't be mapped to any analysis visit. F/U visit will not be included in the summary tables by visit.

Of note, subjects are allowed to have gaps in visits. All data collected will be displayed in listings.

Table 6-1 Analysis Visit Windows

Analysis Visit	Group 1	Group 2	Group 3	Group 4	Group 5	Group 6	Group 7	Group 8
Baseline	≤1*	≤1*	≤1*	≤1*	≤1*	≤1*	≤1*	≤1*
Week 2	2 – 26				2 - 26			
Week 4	27 – 50	2 - 134		2 - 71	27 - 50			2-50
Week 8	51 – 78				51 - 78			51 – 78
Week 12	79 – 106		2 - 148	72 - 106	79 - 106	2 - 148		79 – 106
Week 16	107 – 134			107 - 155	107 - 155			107 – 134
Week 20	135 – 162							135 – 162
Week 24	163 – 190	135 - 316	149 - 316	156 - 211	156 - 211	149 - 211	2 - 316	163 – 190
Week 28	191 – 218							191 – 218
Week 32	219 – 246			212 - 267	212 - 267	212 - 267		219 – 246
Week 36	247 – 274							247 – 274
Week 40	275 – 302			268 - 344	268 - 344	268 - 344		275 – 302
Week 44	303 – 330							303 – 330
Week 48	331 – 358							331 – 358
Week 52	359 – 498	317 - 449	317 - 498	345 - 498	345 - 498	345 - 498	317 - 449	359 – 498
Week 68		450 - 498					450 - 498	

* The first administration of randomized study treatment (first dose) is defined as Day 1.

Group1: ACR components, ESR, High sensitivity C-Reactive protein

Group2: [REDACTED]

Group3: Hematology, blood chemistry, urinalysis, Lipids, [REDACTED]

Group4: [REDACTED]

Group5: LEI, [REDACTED], PASI, [REDACTED]

Group6: Urine pregnancy test

Group7: [REDACTED]

Group8: Vital signs

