The following rules are used to determine the window for an applicable visit post baseline: “Lower limit” = “upper limit of prior applicable visit” + 1. Upper Limit = 0.25*(Week number of current visit)* 7 + 0.75 * (Week number of next applicable visit)*7 + 1. Lower limit of the first applicable visit is always Day 2.

The mapping described above applies to all visits (not just scheduled visits). Repeat and/or unscheduled visits (which will be numbered in the database according to new NCDS standards) will be mapped for analysis purposes in the same way as scheduled visits. This leaves the possibility, then, for multiple measurements within an analysis window. Taking into account the fact that the protocol stipulation is “the study treatment should not be administered less than 14 days from the previous administration” and bi-weekly dosing schedule for Adalimumab, which leads to all visit delays accumulative, the following rule will be used to determine the appropriate measurement to be summarized in the event of multiple measurements within a visit window.

Table 6-2 Rules for flagging variables

Timing of measurement	Type of data	Rule
Baseline	All data	
The last non-missing measurement made prior to or on the date of administration of the first dose of study treatment (the reference start date / Day 1). If a patient did not receive any dose of study treatment then the randomization date will be used. Only date part is considered if just one assessment on Day 1.
 
If there are multiple assessments on Day 1, following rules will apply:
 
 (a) If assessment time exists, 
 - select the last available measurement prior to reference start date/time considering time; - if no measurement prior to reference start date/time considering time, select the earliest measurement post reference start date/time considering time . (b) If assessment time does not exist, select the available measurement from the lowest CRF visit number.
Post-baseline efficacy	All data	
 • The last assessment within the window will be used. • Cases where the same parameter is recorded more than once on the same date will be handled as follows: 
 ○ If time of completion exists the earliest measurement will be used; ○ If time does not exist the measurement from the lowest CRF visit number will be used.

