Post-baseline safety	Summary visit information (e.g. lab)	
 • The last assessment within the window will be used. • Cases where the same parameter is recorded more than once on the same date will be handled as follows: 
 ○ If time of completion exists the earliest measurement will be used; ○ If time does not exist the measurement from the lowest CRF visit number will be used.
Post-baseline safety	Notable abnormalities (e.g. lab)	The most extreme measurement in the window will be used. Note this means a patient can have a notably high and notably low measurement within a window.

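### By-visit laboratory tables take the last value in windows of five to six months, so a repeat test can displace the scheduled value that triggered it, and two scheduled lipid visits share one window

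*SAP*

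**What the plan says.** SAP 6.1 assigns each assessment to an analysis window by study day. One line reads "Group3: Hematology, blood chemistry, urinalysis, Lipids", and that group has three post-baseline windows: Week 12 (Days 2-148), Week 24 (Days 149-316) and Week 52 (Days 317-498). Repeat and unscheduled visits "will be mapped for analysis purposes in the same way as scheduled visits". When a window holds several values, Table 6-2 has two rules for post-baseline safety data:

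- **By-visit summaries, with laboratory data as the example:** "The last assessment within the window will be used".
- **Notable abnormalities:** the most extreme value in the window.

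Protocol 6.5.5 says that clinically significant abnormal results "are to be followed until the values return to normal ranges", or until a valid reason other than a treatment-related adverse event is found. Protocol 7.3 and Appendix 6 set dates for liver repeats, within 48 hours or within a week depending on the finding, and ask for the central laboratory where possible.

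Protocol 9.5.3 plans both kinds of shift table: "Shifts will be presented by visit as well as for most extreme values post-baseline". SAP 2.9.2 adds change from baseline at each visit and box plots over time for neutrophils, liver and lipid parameters.

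**The concern.** Within a window, the last-value rule makes the displayed value depend on the result of the scheduled test. A normal scheduled value prompts no repeat and stays. A clinically significant abnormal one prompts follow-up, and a later sample in the same window takes its place. If the abnormality has resolved by then, the by-visit table shows the resolved value under the scheduled visit's label.

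This matters most for short-lived findings. Protocol 3.6 reports a small increase in neutropenia with secukinumab against placebo and says that "most cases were mild to moderate, transient and reversible". A by-visit display of such a finding could look flatter than the scheduled samples were. It could also disagree with the worst-value tables without a stated reason.

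SAP 6.1 explains its choice by visit delays that accumulate under two-weekly dosing. That is a reason to handle late scheduled visits. It is not a reason to let a repeat replace a scheduled value that exists.

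**Working it through.** **1. Reproduce the windows.** SAP 6.1 gives: upper limit = 0.25 × (current week) × 7 + 0.75 × (next week) × 7 + 1.

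- Week 12, next Week 24: 21 + 126 + 1 = 148, as stated.
- Week 24, next Week 52: 42 + 273 + 1 = 316, as stated.
- Week 52: the limit of 498 does not follow from the formula, because this group has no later visit. With Week 68 as the next visit it would be 91 + 357 + 1 = 449.

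**2. Time for a replacement.** The scheduled day is week × 7 + 1.

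| Window | Days | Width (days) | Scheduled day | Days still open afterwards |
|---|---|---|---|---|
| Week 12 | 2-148 | 147 | 85 | 148 − 85 = 63 |
| Week 24 | 149-316 | 168 | 169 | 316 − 169 = 147 |
| Week 52 | 317-498 | 182 | 365 | 498 − 365 = 133 |

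At 30.44 days per month the widths are 4.8, 5.5 and 6.0 months. SAP 2.9.2 keeps laboratory data only up to last dose + 84 days. For a completer last dosed at Week 50 (Day 351) that is Day 435, so the Week 52 window is in effect 317-435, or 119 days.

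A repeat within 7 days falls on or before Day 92, 176 or 372. Each is inside the same window, so that repeat always replaces a sample taken on the scheduled day.

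**3. Which outputs use the rule.**

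- *Affected:* change from baseline by visit and normal-range shifts by visit. The box plots over time are presumably affected, since no separate selection rule is stated for them.
- *Not affected:* notable abnormalities (most extreme value), CTCAE-grade shifts (worst result), maximum increase and decrease, newly occurring or worsening liver and lipid abnormalities, shifts to the most extreme value, and the listings, which show all data.

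**4. Size.** Let f be the share of scheduled abnormal values that have a normal repeat before the window closes. If nothing else changes, the by-visit abnormal rate becomes rate × (1 − f). The documents give neither f nor the rates. As an assumption only, take 4% against 2% abnormal at the scheduled visit, with the same f in both arms:

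| f | Displayed rates | Difference (points) |
|---|---|---|
| 0 | 4.0% vs 2.0% | 2.0 |
| 25% | 3.0% vs 1.5% | 1.5 |
| 50% | 2.0% vs 1.0% | 1.0 |
| 90% | 0.4% vs 0.2% | 0.2 |

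The difference shrinks while the ratio stays at 2. The formula leaves out replacements in the other direction, from normal to abnormal.

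**5. Patients who leave the study.** Protocol Table 6-1, footnote 13: "Subjects who discontinue the study should be scheduled for an End-of-Study study visit, 4 weeks after their last study treatment administration". SAP 6.1 excludes only follow-up visits from the mapping, so this sample is mapped by its day. It shares a window with an earlier scheduled value if the last dose falls on Days 85-120 (148 − 28 = 120) or 169-288 (316 − 28 = 288). That is 35 + 119 = 154 of 351 dosing days, or 44%. If 10% to 20% leave evenly over time and all attend this visit (both assumed), 4.4% to 8.8% of patients are affected.

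**6. Lipids.** Protocol Table 6-1, as its columns read in the extracted text, schedules post-baseline lipids at Weeks 8, 16, 24 and 52. Weeks 8 and 16 are Days 57 and 113, both inside Days 2-148. With both samples present, the Week 8 value is dropped and the Week 16 value is labelled Week 12, even with no repeat.

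**The case against.** The strongest reply is that abnormality reporting is already protected. The row of Table 6-2 directly below takes the most extreme value, CTCAE shifts take the worst, clinically significant results are recorded as adverse events (Protocol 7.1), and everything is listed. A reader might infer that transient neutropenia or raised liver enzymes would vanish from the report. The documents do not support that. This part of the reply stands in full.

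Other parts also stand:

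- **The replaced share is unknown.** One might suppose that the last value is usually the recovered one. Nothing in the documents shows this. Protocol 6.5.5 covers only clinically significant values and lets follow-up stop for a valid reason. Dated repeat orders exist for liver tests only, and mild to moderate neutropenia need not trigger a repeat.
- **The net direction is not proven.** A sample prompted by illness can replace a normal scheduled value with an abnormal one.
- **The End-of-Study sample is not a clear off-drug value.** Samples are drawn before dosing, so in the secukinumab arm the Week 12 and Week 24 samples also come 4 weeks after the last active doses, at Weeks 8 and 20. The End-of-Study sample also lies within the SAP's on-treatment period. What remains is a visit-labelling issue.
- **The stakes are descriptive.** No laboratory hypothesis test is planned, the rule is the same in both arms, and a few replaced values barely move means, medians or quartiles.

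It can also be said that a later repeat is the confirmed value, since Protocol 7.3 orders liver repeats to confirm elevation or resolution. That stands only in part. A repeat showing resolution describes a later time, and an existing scheduled result should not be relabelled with it.

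**Conclusion.** The point holds for by-visit displays only. The last-value rule, the mapping of repeats and the window limits are stated in the SAP, and the limits of Days 148 and 316 reproduce exactly. Together with the protocol's follow-up of abnormal results, they make the choice of displayed value depend on the outcome, which is avoidable. By-visit shift counts, minima and maxima are the figures most exposed.

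The size cannot be derived from the documents: f may lie anywhere from 0 upward, and the table of rates above is illustration only. The box-plot point is an inference.

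The lipid point needs no assumption about repeats. It rests on reading the Table 6-1 columns from extracted text, which should be checked against the original table.

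Nothing here touches the efficacy analysis or the worst-value safety analyses. It is a cheap improvement to the SAP.

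**What to change.** 1. **SAP Table 6-2, row for post-baseline safety, summary visit information.** For laboratory data, use the value from the scheduled (nominal) visit. Only if it is missing or could not be analysed, use the value closest to the target day. Repeat, unscheduled and End-of-Study samples do not overwrite an existing scheduled value. State that the box plots follow the same rule.
2. **SAP Table 6-1.** Give lipids their own window group from the SAP's formula: Week 8, Days 2-99 (14 + 84 + 1 = 99); Week 16, Days 100-155 (28 + 126 + 1 = 155); Week 24, Days 156-316; Week 52, Days 317-498. The first change needs this one, because in the present window both lipid visits are scheduled and each lies 28 days from Day 85.
3. **Leave unchanged** the most-extreme rule, with all repeats and unscheduled samples, for notable abnormalities, CTCAE worst grade and worst-value shifts.

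The cost is one reworded row, one added window group and one selection flag in the laboratory dataset. The downside is small: an unconfirmed laboratory error at a scheduled visit stays in the by-visit display unless the sample was reported as not analysable.

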6.2 Statistical methodology and assumptions

6.2.1 Analysis of continuous data

6.2.1.1 Summary statistics for continuous data

Summary statistics (including N, mean, standard deviation, minimum, lower quartile, median, upper quartile, maximum) will be provided for continuous data by visit and treatment group.

6.2.1.2 Mixed-effects repeated measures model

Endpoints with continuous data type expected to be normally distributed (e.g. ██████████) will be analyzed using a mixed-effects repeated measures model (MMRM) with treatment, and analysis visit as factors; and weight, baseline value, treatment by visit and baseline by visit interactions as covariates. An unstructured covariance structure will be assumed for this model. The significance of the treatment effects for secukinumab regimen at different analysis visits will be determined from the comparisons performed between secukinumab regimen and adalimumab at the appropriate analysis visits.

SAS code for mixed model:

```
proc mixed data=aaa;
class TRT USUBJID AVISITN;
model CHG=TRT AVISITN WEIGHT BASE TRT*AVISITN BASE*AVISITN
      / s ddfm=kr;
lsmeans TRT*AVISITN / diff cl;
repeated AVISITN / type=un subject=USUBJID;
Run;
```

In case the MMRM model does not converge the following sequential steps will be used:

1. change ddfm=kr to ddfm=bw. If still no convergence, perform step 2.
2. change type=un to type=cs. If still no convergence, perform step 3.
3. remove covariates in the following order until convergence: WEIGHT, BASE*AVISITN.

Details of Implementation

Steps in implementing MMRM for continuous variables

1. For each continuous endpoint, set the data collected after patient discontinued study treatment to missing.
2. For each continuous endpoint, set data collected after patient took cDMARDs after Week 36 to missing.
3. Proceed with MMRM

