- H₃: secukinumab 300 mg is not different to adalimumab regimen with respect to monotherapy ACR50 response at Week 52
- H₄: secukinumab 300 mg is not different to adalimumab regimen with respect to the change from baseline in HAQ-DI[®] at Week 52
- H₅: secukinumab 300 mg is not different to adalimumab regimen with respect to monotherapy resolution of enthesitis based on LEI at Week 52

The graphical approach of ([Bretz et al 2009](#)) for sequentially reject testing procedures is used to illustrate the testing strategy:

Figure 2-1 Hierarchical testing strategy

The family-wise error rate will be set to two-sided $\alpha=5\%$ and it will be controlled with the proposed hierarchical testing strategy. If H1 is rejected at α , each of the following hypotheses will be tested at α . If H2 is rejected at α , H3 will be tested at α and so on.

Monotherapy ACR50 at Week 52

Monotherapy response at Week 52 to ACR50 in the FAS will be evaluated using a logistic regression model with treatment as a factor and weight as a covariate.

Monotherapy PASI90 response

[figure not shown]
Monotherapy PASI90 response at Week 52 will be evaluated using a logistic regression model with treatment as a factor and weight as a covariate based on Psoriasis subset.

Physical function (HAQ-DI[®])

Between-treatment differences in the change in HAQ-DI[®] will be evaluated using a MMRM with treatment regimen, analysis visit as factors, and weight and baseline HAQ-DI[®] score as continuous covariates. Treatment by analysis visit and baseline by analysis visit will be included as interaction terms in the model. An unstructured covariance structure will be assumed for this model. The significance of the treatment effects for secukinumab regimen at different analysis visits will be determined from the pairwise comparisons performed between secukinumab regimen and adalimumab at the appropriate analysis visits.

Monotherapy Resolution of enthesitis

Monotherapy resolution of enthesitis based on LEI at Week 52 will be evaluated using a logistic regression model with treatment as a factor and weight as a covariate based on Enthesitis subset (LEI).

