****Buttocks are assessed as part of the Lower limbs (L) body region.

[figure not shown]
Because the head and neck, upper limbs, trunk and lower limbs correspond to approximately 10%, 20%, 30% and 40% of the body surface area, respectively, the PASI score is calculated using the formula:

[figure not shown]
$$\text{PASI} = 0.1(\text{E}_H + \text{I}_H + \text{D}_H)\text{A}_H + 0.2(\text{E}_U + \text{I}_U + \text{D}_U)\text{A}_U + 0.3(\text{E}_T + \text{I}_T + \text{D}_T)\text{A}_T + 0.4(\text{E}_L + \text{I}_L + \text{D}_L)\text{A}_L$$

[figure not shown]
The keys for the letters are provided in [Table 2-7](#).

[figure not shown]
PASI scores can range from a lower value of 0, corresponding to no signs of psoriasis, up to a theoretic maximum of 72.0. The total score comes from eCRF.

3 Sample size calculation

A family-wise error will be set to two-sided $\alpha=0.05$ to control for type I error. The primary objective of secukinumab 300 mg versus adalimumab with respect to ACR50/ACR20 response at Week 52 will be tested at a two-sided 0.05 alpha level.

An ACR20 response rate of about 50% for the TNF α inhibitor naïve without MTX use (monotherapy) population at week 48 was reported in Humira study ([Gladman 2007](#)). The response on secukinumab 300 mg is estimated to be 62% in the TNF α inhibitor naïve monotherapy population based on the lower bound of 80% confidence interval of Meta-analysis results of the study FUTURE2 ([McInnes 2015](#)) and unpublished study FUTURE3. With 425 subjects per treatment group there would be approximately 94% power to detect a treatment difference of 12% at a two-sided 0.05 alpha level in ACR20 response rates (Chi Square test, NQuery 7.0) between secukinumab 300 mg and adalimumab in the evaluation of the primary efficacy hypothesis at Week 52. The overall sample size will be 850 patient for a randomization ratio of 1:1 (secukinumab 300mg 425 patients, and adalimumab 425 patient). The estimated power with the chosen sample size for other efficacy endpoints based on the data available for adalimumab and meta-analysis results of the study FUTURE2 and study FUTURE3 are summarized in [Table 3-2](#).

Table 3-1 Assumption for sample size and power calculation

Endpoint	Secukinumab 300 mg expected values	Adalimumab (N=76) observed values
ACR20	62%	50%
PASI90	63%	38% (N=40)
ACR50	49%	38%
HAQ-DI change*	-0.59 (0.5)	-0.4 (0.5)(N=61)
Resolution of enthesitis	61%	33%

*mean (standard deviation)

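### If the unstructured HAQ-DI model fails to converge, the fallback to homogeneous compound symmetry with model-based standard errors holds 5% at Week 52 only if the Week 52 variance equals the visit average

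*SAP*

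**What the plan says.** SAP 2.7 places HAQ-DI change at Week 52 fourth in a fixed sequence meant to hold family-wise error at a two-sided 5%. Each hypothesis is tested at full alpha once the one before it is rejected, and rejecting H4 opens H5 (resolution of enthesitis). The method for H4 is that the change "will be evaluated using a MMRM with treatment regimen, analysis visit as factors"; the model also carries weight, the baseline score, and interactions of visit with treatment and with baseline.

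SAP 6.2.1.2 gives the model: "An unstructured covariance structure will be assumed for this model", coded as "repeated AVISITN / type=un subject=USUBJID". The printed PROC MIXED call has no EMPIRICAL option, so standard errors are model-based. For non-convergence it lists three sequential steps:

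1. The first alters only the denominator degrees of freedom: "change ddfm=kr to ddfm=bw. If still no convergence, perform step 2".
2. The second replaces the covariance structure and leaves the mean model as it was: "change type=un to type=cs. If still no convergence, perform step 3".
3. The third simplifies the mean model, dropping weight first and the baseline-by-visit interaction after it.

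No intermediate covariance structure, robust standard error or numerical remedy is given. SAP 2.6.3 sends continuous efficacy variables in general to this section, so the rule is not confined to HAQ-DI.

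**The concern.** In SAS, type=cs is the homogeneous form: one variance for all visits and one covariance for all pairs. With model-based standard errors, the Week 52 comparison is judged against the variance averaged over visits. If Week 52 is more variable than the average visit, the standard error is too small and the test rejects too often. If it is less variable, the test is conservative. Rising variance is plausible for a change from baseline, because early scores lie close in time to the baseline value, but the documents do not show it.

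The test at stake is confirmatory, and a false rejection of H4 also opens H5. A written contingency is hard to replace credibly after unblinding, so it should hold its level in the case it was written for.

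Step 1 is a separate and lesser matter. The ddfm option sets denominator degrees of freedom (and, for Kenward–Roger, a standard-error adjustment) after the covariance has been estimated. It does not enter the likelihood being maximised, so it cannot turn a failed fit into a converged one.

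**Working it through.** **Inputs.** 425 per arm; HAQ-DI change −0.59 against −0.40, SD 0.5 in both arms (SAP Section 3, Table 3-1). HAQ-DI is an ACR component, so it follows visit-window Group 1 in SAP Table 6-1: Weeks 2 and 4, then every 4 weeks to Week 52, which is 14 post-baseline visits. Visit-level SDs, correlations and dropout are not given and are assumed below.

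**The plan's own figure.** Standard error = 0.5 × √(2/425) = 0.0343. Then 0.19/0.0343 = 5.54, and power = Φ(5.54 − 1.96) = 99.98%, consistent with the stated 99%.

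**Parameters.** Unstructured: 14 × 15/2 = 105. Homogeneous compound symmetry: 2.

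**Type I error under the fallback.** With complete data and visit-specific treatment and baseline effects, the two covariance structures give essentially the same Week 52 estimate, so only the standard error differs. Let r = SD at Week 52 / root-mean-square SD over the 14 visits. Then

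type I error = 2 × [1 − Φ(1.96/r)].

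Example: if the SD rises in equal steps per visit from 0.40 to 0.50, the mean variance is 0.2035, its root is 0.451, r = 0.5/0.451 = 1.108, 1.96/r = 1.768, and the error is 7.7%.

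| Assumed SD pattern, ending at 0.50 | Starting SD | Type I error |
|---|---|---|
| Falls linearly | 0.60 | about 3% |
| Flat | 0.50 | 5.0% |
| Rises, level from Week 12 | 0.40 / 0.35 / 0.30 | 5.7 / 6.0 / 6.4% |
| Rises, level from Week 16 | 0.40 / 0.35 / 0.30 | 5.9 / 6.3 / 6.8% |
| Rises, level from Week 24 | 0.40 / 0.35 / 0.30 | 6.3 / 6.9 / 7.6% |
| Rises linearly to Week 52 | 0.40 / 0.35 / 0.30 | 7.7 / 9.4 / 11.3% |

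The linear rise is by visit number (r = 1.108, 1.169, 1.235); scaling it by week gives 7.8, 9.6 and 11.5%. The levelling-off rows are scaled by week.

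**Simulation.** The SAP mean model was fitted by REML with compound symmetry: 850 patients, 14 visits, Week 52 SD 0.5, assumed correlation 0.8 per 12 weeks, 2,000 runs per scenario, Monte Carlo error about 0.5 points at 5%. SD changes linearly by week.

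| SD Week 2 / SD Week 52 | Complete data | 20% random dropout |
|---|---|---|
| 1.0 | 5.8% | 6.3% |
| 0.8 | 7.1% | 9.3% |
| 0.6 | 11.8% | 13.8% |
| 1.2 | not run | 4.2% |

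Two further scenarios gave 8.9% (ratio 0.6, square-root growth, complete data) and 10.7% (ratio 0.8, 20% outcome-dependent dropout under MAR). With sandwich standard errors on the same compound-symmetry fits, error was 4.5% to 6.0% in all nine scenarios. Heterogeneous structures were not simulated, and SAS was not run.

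**Unconditional effect.** The documents give no fallback probability. Suppose it is 1% or 5%, independent of the test result, with the unstructured fit at exactly 5%. For the linear-rise cases:
- 1%: 0.99 × 5% + 0.01 × (7.7% to 11.3%) = 5.03% to 5.06%
- 5%: 0.95 × 5% + 0.05 × (7.7% to 11.3%) = 5.1% to 5.3%

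**The case against.** The best case for the plan is that the rule will probably never be used. With about 850 patients, 105 covariance parameters should be estimable. H4 is reached only after H1 to H3 are rejected, and the sequence is fixed in advance, so it leaves no room for a data-driven choice. H1, H2, H3 and H5 use logistic regression and do not rest on this model. All of that stands.

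The objection on size also stands. The documents give a single HAQ-DI SD, and linear growth right up to Week 52 is a severe pattern. An SD that levels off is no less plausible and gives much smaller inflation, and a falling SD makes the test conservative. In the other direction, SAP 6.2.1.2 sets data after treatment discontinuation to missing, so Week 52 will be incomplete, and the simulated dropout raised the error in the growth cases.

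A reader might infer that H4 will be tested at 8% to 11%, or that the trial's family-wise error control fails. The documents support neither reading: those figures apply only if the fallback is reached and only under assumed linear growth. A reader might also infer that step 1 does damage. It does not. It is ineffective, the sequence simply moves on, and the different degrees-of-freedom method is negligible at this sample size.

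What the objection does not remove is that a rule written for a confirmatory test gives a wrong standard error in the one situation where it applies, unless the variances happen to match.

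**Conclusion.** The point holds as a conditional one. If the unstructured HAQ-DI model fails and step 2 is used, the test holds its nominal 5% at Week 52 only if the Week 52 variance equals the 14-visit average. With complete data and the assumed SD patterns, the conditional error runs from about 3% to 11.3%, so the direction as well as the size depends on figures the documents do not give. The unconditional effect on H4 is small, because non-convergence is unlikely. Planned power and the unstructured analysis are unaffected. This is a low-probability weakness worth correcting because the correction is nearly free. It is not evidence that the main analysis is invalid.

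**What to change.** In SAP 6.2.1.2:

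- Replace step 1 with a numerical step that can affect convergence, such as supplied starting values or Fisher scoring.
- Before any homogeneous structure, place at least one with visit-specific variances, for example heterogeneous Toeplitz or heterogeneous compound symmetry. The choice and order among such structures is partly preference.
- For any structured fallback, use empirical (sandwich) standard errors with ddfm=bw.

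The cost is a few lines of text and code, with a slightly wider interval in some cases if a fallback is used. One limit should be stated in the SAP: sandwich standard errors do not remove bias in the estimate from a misspecified covariance when data are missing at random. That is a further reason to try a richer structure first.
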